8.3.7.1 Papanicolaou Test

If a previous PAP smear report is available and the results meet the local guidelines, no additional tests are needed. If additional PAP smear or equivalent cervical cytology in combination with HPV testing are required, they will be performed at site, following the local guidelines at Visit 1.

If the results of the PAP smear are abnormal the participant will be informed of the results and advised as to any medically appropriate follow-up. A participant would be excluded if the participant has any of the following cervical pathology: atypical squamous cells ASC-H, low-grade squamous intraepithelial lesion, high-grade squamous intraepithelial lesion, atypical glandular cells [any type], squamous cell carcinoma, or adenocarcinoma [in situ or invasive]) or has a high-risk HPV.

8.3.7.2 Sexually Transmitted Infection Panel

The STI panel will be performed, if indicated and participants will be tested for gonorrhea and chlamydia unless they were screened within the past 3 months and have no new sexual partner. Testing for trichomonas and bacterial vaginosis will only be required if abnormal vaginal discharge is present. Testing will be performed locally at Visit 1 and may be repeated during the study as needed.

8.3.7.3 Serum Hormone Tests

CCI

CCI

8.3.8 Pregnancy Testing

Women of childbearing potential should only be included after a confirmed menstrual period and a negative highly sensitive urine/serum pregnancy test.

Additional pregnancy testing should be performed at times specified during the treatment period and at safety follow-up, corresponding to protocol-defined time frame in Section 5.1 after the last dose of study treatment and as required locally.

Pregnancy testing will be performed whenever a menstrual cycle is missed or when pregnancy is otherwise suspected.

CCI

8.4 Adverse Events, Serious Adverse Events, and Other Safety Reporting

The definitions of an AE and SAE, as well as the method of recording, evaluating, and assessing causality of AE and SAE and the procedures for completing and transmitting AE and SAE can be found in [Appendix 4](#).

Adverse events and SAEs will be reported by the participant (or, when appropriate, by a caregiver, surrogate, or the participant's legally authorized representative).

The Investigator and any designees are responsible for detecting, documenting, and recording events that meet the definition of AEs and SAEs. Investigators remain responsible for following up AEs and SAEs for outcome according to Section 8.4.3. Investigators remain

responsible for following up events that are serious, considered related to the study treatment or study procedures, or that caused the participant to discontinue the study treatment or study procedures, or that caused the participant to discontinue the study treatment or withdraw from the study (see Section 7.0).

The Investigator, who is a qualified physician, will assess events that meet the definition of an AE or SAE with respect to seriousness, severity, and causality.

For any guidance regarding AE/SAE reporting, the Investigator should contact the Medical Monitor.

8.4.1 Time Period and Frequency for Collecting AE and SAE Information

All AEs and SAEs will be collected from the signing of the ICF until EOS at the time points specified in the SoA (Section 1.3).

All SAEs will be recorded and reported to the Sponsor or designee immediately and under no circumstance should this exceed 24 hours of the Investigator's awareness of the event, as indicated in Appendix 4. The Investigator will submit any updated SAE data to the Sponsor or designee within 24 hours of their awareness of the updated information.

From the time of screening (V1) through EOS/discontinuation, which is 30 days after last intake of study treatment, all AEs, SAEs, and other reportable safety events must be reported by the Investigator.

Additionally, any SAE brought to the attention of an Investigator at any time outside the period specified in the previous paragraph must be reported immediately (within 24 hours of learning about the event) to the Sponsor if the event is considered related to study treatment.

Investigators are not obligated to actively seek information on AEs or SAEs after conclusion of the study participation. However, if the Investigator learns of any SAE, including a death, at any time after a participant has been discontinued from the study, the event/cause of death is considered to be reasonably related to the study treatment or study participation, the Investigator must promptly notify the Sponsor or designee.

All initial and follow-up AEs, SAEs, and other reportable safety events will be recorded and reported to the Sponsor or designee within the time frames as indicated in Table 7.

The method of recording, evaluating, and assessing causality of AE and SAE and the procedures for completing and transmitting SAE reports are provided in Appendix 4.

Table 7 Reporting Time Periods and Time Frames for Adverse Events and Other Reportable Safety Events

Type of Event	Reporting Time Period: Screening (V1) to Pre-Treatment Allocation (C)	Reporting Time Period: Treatment Allocation (C) through Protocol-specified Follow-up Period	Time Frame to Report Event and Follow-up Information to Sponsor:
Nonserious Adverse Event (NSAE)	Report if: 
 Due to protocol-specified procedure Causes exclusion 	Report all	Per data entry guidelines
Serious Adverse Event (SAE)	Report if: 
 Due to protocol-specified procedure Causes exclusion 	Report all	Within 24 hours of learning of event
Pregnancy/Lactation Exposure	Report if: 
 Participant has been exposed to any protocol-specified procedure 	Report all	Within 24 hours of learning of event
CCI			
Overdose	Report if: 
 receiving CCI or other medication (including Rescue Medication) 	Report all	
All overdose events associated with SAE (including intentional suicidal/self-harming intent) must be reported within 24 hours by completing a SAE form
 
Overdose events associated with a non-serious AE must be reported within 5 calendar days of learning of event
 
All other overdose cases not associated with AE/SAE must be captured in the appropriate section of eCRF

8.4.2 Method of Detecting AEs and SAEs

Care will be taken not to introduce bias when detecting AEs and/or SAEs. Open-ended and nonleading verbal questioning of the participant is the preferred method to inquire about AE occurrences.

8.4.3 Follow-up of AEs, AESIs, and SAEs

After the initial AE/SAE report, the Investigator is required to proactively follow each participant at subsequent visits/contacts. All AEs, SAEs, and other reportable safety events, including pregnancy complications/outcomes ([Appendix 4](#)) and exposure during breastfeeding, and AESIs, must be followed until resolution, stabilization, until the event is otherwise explained, or the participant is lost to follow-up (as defined in [Section 7.4](#)). In addition, the Investigator will make every attempt to follow all nonserious AEs that occur in eligible (allocated to treatment) participants for outcome. Further information on follow-up procedures is given in [Appendix 4](#).

8.4.4 Regulatory Reporting Requirements for SAEs

- Prompt notification by the Investigator to the Sponsor of an SAE is essential so that legal obligations and ethical responsibilities towards the safety of participants and the safety of a study treatment under clinical investigation are met.
- The Sponsor has a legal responsibility to notify both the local regulatory authority and other regulatory agencies about the safety of a study treatment under clinical investigation. The Sponsor will comply with country-specific regulatory requirements relating to safety reporting to the corresponding regulatory authority, IRB/IEC, and Investigators.
- Investigator safety reports must be prepared for suspected unexpected serious adverse reactions (SUSAR) according to local regulatory requirements and Sponsor policy and forwarded to Investigators as necessary. When an investigator receives a SUSAR, it should be reported to the IRB/IEC immediately or within 24 hours.
- SUSAR reports will be submitted electronically (gateway to gateway) from the sponsor's safety database to the EudraVigilance Clinical Trial Module, in accordance with the EU Clinical Trial Regulation.
- An Investigator who receives an Investigator safety report describing an SAE or other specific safety information (eg, summary or listing of SAEs) from the Sponsor will review and file it along with the IB and will notify the IRB/IEC, if appropriate according to local requirements.

8.4.5 Pregnancy

If any participant becomes pregnant during the study, the study site must discontinue the participant from the study treatment immediately and have her return for an early-study termination visit. The Investigator must inform the participant of her right to receive treatment information. If the participant chooses to receive unblinded treatment information, the individual blind should be broken, and the treatment assignment provided to the participant. The study team will remain blinded to the participant's treatment assignment.

If the participant agrees, the Investigator should notify the participant's primary care physician of the pregnancy and provide details of the participant's participation in the study and treatment

(blinded or unblinded, as applicable).

- Details of all pregnancies will be collected based on the schedule outlined in [Appendix 5](#).
- If a pregnancy is reported, the Investigator should inform the Sponsor within 24 hours of learning of the pregnancy and should follow the procedures outlined in [Appendix 4](#) and [Appendix 5](#).
- Abnormal pregnancy outcomes (eg, spontaneous abortion, fetal death, stillbirth, congenital anomalies, ectopic pregnancy) are considered SAEs.

8.4.6 Adverse Events of Special Interest

Selected adverse events (nonserious and serious) that might be potential precursors or prodromes for more serious medical conditions will be considered as AESIs for this protocol. All AESIs must be reported as AEs in the eCRF.

CCI

CCI

8.5 Pharmacokinetics

8.5.1 Collection of Samples

Samples for determination of OG-6219 and its primary, active metabolite FOR-1011 concentration will be collected for all participants as per the SoA in Section 1.3 and in Table 8.

Samples of approximately 2 mL of blood will be collected at each PK timepoints for measurement of plasma concentrations of OG-6219 and FOR-1011. Instructions for the collection, handling, storage, and shipment of biological samples (plasma) will be provided separately in a laboratory manual by the Sponsor or its designee. The actual date and time (24-hour clock time) of each sample will be recorded. The time and date of each study treatment administration on the visit days will be recorded for all participants.

Samples will be used to evaluate the PK of OG-6219 and FOR-1011. Each timepoints for PK will yield one primary and one backup sample. Samples collected for analyses of OG-6219 and FOR-1011 (plasma) concentrations may also be used to evaluate safety or efficacy aspects related to concerns arising during or after the study and/or for modeling and simulation of

exposure and/or exposure versus response.

Table 8 Schedule of Pharmacokinetics Sampling

CCI

CCI

8.5.2 Determination of Drug Concentration

Samples for the determination of OG-6219 and FOR-1011 in plasma will be analyzed using an appropriate validated bioanalytical method. Full details of the bioanalytical method will be described in a separate Bioanalytical Report.

All samples still within the known stability of the analyte of interest at the time of receipt by the bioanalytical laboratory will be analyzed.

Remaining plasma samples may be participated to further analysis by the Sponsor or designee for the purpose of development of additional bioanalytical assays and/or for metabolite analysis in human plasma.

Drug concentration information that may unblind the study will not be reported to study site or blinded personnel until the study has been unblinded.

Any unexpected below the limit of quantification must be timely reported to the Sponsor or its delegate.

8.6 Pharmacodynamics

Blood samples for PD will be collected for all participants as per the SoA in Section 1.3. Instructions for the collection, handling, storage, and shipment of biological samples will be provided separately in a laboratory manual by the Sponsor or designee.

The PD/Safety assessment of CCI will be determined at the times indicated in the SoA (Section 1.3).

CCI

8.7 Genetics

Genetics are not evaluated in this study.

8.8 Biomarkers

CCI

CCI

For the CCI, blood specimens will be collected as per the times indicated in the SoA (Section 1.3).

8.9 Health Economics/Medical Resource Utilization and Health Economics

Health Economics/Medical Resource Utilization and Health Economics parameters are not evaluated in this study.

8.10 Changes to Study Procedures Due to Exceptional circumstances

Exceptional circumstances

Exceptional circumstances are rare events that may cause disruptions to the conduct of the study. Examples include pandemics or natural disasters. These disruptions may limit the ability of the Investigators, participants, or both to attend on-site visits or to conduct planned study procedures.

Implementing changes under exceptional circumstances

In an exceptional circumstance, after receiving the Sponsor's written approval, sites may implement changes if permitted by local regulations.

COVID-19

The following information provides guidance regarding changes to the study procedures that could be implemented for study participants or study sites affected by the COVID-19 public health emergency. This guidance takes references from the FDA Guidance on Conduct of Clinical Trials of Medical Products during COVID-19 Public Health Emergency—Guidance for Industry, Investigators, and Institutional Review Boards, March 2020, updated 03 June 2020, and the European Medicines Agency Guidance on the Management of Clinical Trials During the COVID-19 Pandemic, Version 3 (28 April 2020).

As the COVID-19 pandemic may peak in different regions at different times and restrictions implemented by local laws and recommendations may vary, any decision on participation and procedural changes should be made on a case-by-case basis by the Investigator in consultation with the study team and the medical team as needed, while maintaining participant safety and confidentiality as the priority.

Procedural changes due to COVID-19 may include the following:

- Participants must be fully vaccinated with approved COVID-19 vaccines as per the country-specific requirements.
- Missed study site visits or participant withdrawals due to COVID-19 must be recorded on the eCRF. Participants who discontinued from Screening or **CCI** due to COVID-19-related factors but were otherwise qualified to participate in the study may be rescreened (see [Appendix 2](#)). Any rescreening must be approved by Medical Monitor.
- Allow electronic clinical outcomes assessments typically scheduled for completion at the study site to be completed at home if a study site visit cannot occur.
- In specific circumstances and with Sponsor approval, it may be allowed to transfer the participants to study sites away from the risk zones or closer to their homes (either to new study sites or sites already participating in the study).

Deviations from the protocol-specified procedures (eg, laboratory assessments) will be recorded as related to COVID-19.

9.0 STATISTICAL CONSIDERATIONS

9.1 Statistical Hypotheses

CCI

Where appropriate, variables will be summarized descriptively (frequency and percent will be summarized for categorical variables; n, mean, standard deviation [SD], median, minimum, and maximum will be presented for continuous variables) by study time point (cycle or visit) and by treatment group.

9.1.1 Multiplicity Adjustment

No adjustment for multiplicity is planned since this is a Phase 2a/b study; the comparisons of interest are for each active dose group versus control. Secondary, and exploratory endpoints will thus be tested at CCI and nominal p-values will be provided.

9.2 Analysis Sets

- Full Analysis Set (FAS)—all participants randomized
- Modified Full Analysis Set (MFAS)—all participants randomized who receive at least 1 dose of study treatment and who completed at least 1 subsequent diary entry CCI
- Per Protocol (PP)—all participants in the MFAS who completed at least one treatment cycle with no major protocol deviations that may impact the interpretation of the primary efficacy endpoint
- Safety (SAF)—all participants who received at least 1 dose of study treatment
- Safety Follow-up Analysis Set (SFAS)—all participants randomized who receive at least 1 dose of study treatment and have at least 1 diary entry CCI after the date of last treatment
- PK Analysis Set: The PK analysis set is a subset of the Safety analysis set (SAF) and will include all participants who received at least a dose of OG-6219 and have at least 1 quantifiable OG-6219 or FOR-1011 concentration.
- Pharmacokinetic Analysis Set for Noncompartmental Analysis: The PK analysis set for noncompartmental analysis (NCA) will include all participants in the PK analysis set CCI chose intensive PK sampling CCI and have sufficient samples to determine at least one PK parameter for OG-6219 or FOR-1011. Intensive PK sampling is optional where a separate consent would be provided.
- PD Analysis Set—The PD analysis set is a subset of the SAF and will include all participants who received at least a dose of OG-6219 or Placebo and have at least 1 quantifiable PD endpoint without protocol deviations or events affecting the PD results.

Analyses will be performed in the respective analysis populations (safety analyses in the safety set, PK analysis in the PK analysis set and PK analysis Set for NCA, PD analysis in the PD analysis set, and efficacy analyses in the MFAS for on-treatment efficacy, SFAS for post-treatment efficacy, and select efficacy analyses in the FAS and/or PP analysis set).

9.3 Sample Size Considerations

Approximately CCI pre-menopausal females aged 18 to 49 years old (inclusive), who have been surgically diagnosed with endometriosis within the last 4 months to 10 years prior to V1, will be screened to achieve 380 randomly assigned to the study treatment (C participants in each group). A total of 380 participants will provide CCI power to detect a difference CCI between an OG-6219 dose group and Placebo in change from baseline to TRC3 of mean OPP, assuming a common SD of 2.2. This power calculation is based on a CCI and a dropout rate of CCI.

A minimum subset of C participants per group CCI will be enrolled for optional intensive PK sampling for the entire duration of the study.

9.4 Statistical Analyses

9.4.1 General Considerations

The SAP will be developed and finalized before database lock and will describe the participant analysis sets used for each analysis, methods of analysis, and procedures for accounting for missing, unused, and spurious data. This section is a summary of the planned statistical analyses of the primary, secondary, and exploratory endpoints.

All statistical models will evaluate pairwise treatment comparisons between Placebo and a single OG-6219 dose arm. No comparisons will be made between different dose levels.

All data will be listed, and summary tables using descriptive statistics over time will be provided. Summary statistics will be presented by treatment group.

9.4.2 Primary Endpoint Analysis

The primary endpoint will be the mean change from BC of the average daily OPP score during TRC3. The OPP will be calculated for each cycle as the total of OPP scores reported during the cycle divided by the number of days during the cycle in which the score was reported. For participants who discontinue early, their last cycle will be associated with the cycle number at entry into the cycle. The primary analysis will be conducted using the MFAS and will use a longitudinal model. The response vector for the model will be change from BC in the average OPP during TRC1, TRC2, and TRC3. Model terms will include the respective baseline, treatment, time (ie, cycle), and treatment-time interaction, allowing for the inclusion of individual outcomes over time (cycle). An unstructured error structure will be assumed. If

nonconvergence is encountered, compound symmetry (CS) and first-order autoregressive AR(1) error structures will be considered.

Least squares mean change from baseline for each treatment group, with corresponding standard errors will be provided. Estimated treatment differences (each active treatment group versus Placebo) with corresponding 95% CI and 2-sided p-values will also be provided for each active treatment group. No missing data will be imputed for the primary analysis.

Supportive analyses will be conducted using an analysis of covariance (ANCOVA) on the change from baseline to the TRC3, with treatment as a fixed factor and baseline OPP as a covariate.

The primary longitudinal and ANCOVA models will be repeated using the PP set.

A completers analysis will be performed for those participants who completed all 3 treatment cycles. Details regarding additional sensitivity and subgroup analyses of the primary efficacy endpoint will be described in the SAP.

9.4.3 Secondary Endpoint Analysis

Secondary endpoints assessing change in continuous endpoints over time (either measurements within the cycle or at an individual visit) will use longitudinal models as described for the primary endpoint and/or ANCOVA models. Changes from SC to SFC will be compared using ANCOVA models in the SFAS. Select longitudinal models which focus on TRC1 and TRC2 may exclude TRC3 from the model. An unstructured error structure will be assumed for all longitudinal models. If nonconvergence is encountered, CS and AR (1) error structures will be considered.

Definitions corresponding to the incidence of clinically significant values will be provided in the SAP.

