4. To evaluate the daily use of Sponsor provided rescue medication taken for ERP at TRC1, TRC2, and TRC3	
 Change from BC to TRC1, TRC2, and TRC3 in the mean number of tablets of rescue medication for ERP Change from BC to TRC1, TRC2, and TRC3 in the proportion of days participant has used rescue medication for ERP

Objectives	Endpoints
5. To evaluate the change in the PGI-S Score at different time points	• Change in PGI-S Score from C to Phone Contact CCI
6. To evaluate the change in the PGI-C Score in different time points	• Percentage of participants with any improvement on the PGI-C at TRC1, TRC2, and TRC3
7. To evaluate the change in the EHP-30 domains (CCI) from BC to TRC3	• Change from BC to TRC3 in the EHP-30 Domain Scores
Secondary Safety Endpoints	
8. To assess the incidence of clinically significant ^d changes from V1 to C in bone biomarkers: ○ CCI ○	• Mean change from V1 to C in bone biomarker levels
9. To assess the incidence of any clinically significant ^d changes in laboratory parameters from V1 to CCI	• Proportion of participants with clinical parameters of significance from V1 to CC
10. To assess vaginal bleeding pattern over the 3 menstrual cycles (TRC1, TRC2, and TRC3) as captured in the eDiary	• Mean change from BC to TRC1, TRC2, TRC3 in the percentage of days with vaginal bleeding
11. To assess any potential change in the ECG parameters at CCI	• ECG parameter changes at CCI
Secondary PD / PK Endpoints	
12. To assess the change from CCI in serum hormone ^b concentrations	• Mean change from CCI in serum hormone levels
13. To assess any difference in serum hormone ^b concentrations at C between active treatment versus placebo	• Serum hormone levels comparing Group A (CCI BID), B (CCI BID), C (CC BID) with Group D (Placebo)
14. To assess any difference in serum hormone ^b concentrations at C between active treatment versus placebo	• Serum hormone levels at V7 comparing Group A (CCI BID), B (CCI BID), C (CCI BID) with Group D (Placebo)
15. To assess the PK of orally administered OG-6219 and the active metabolite FOR-1011 using sparse and intensive ^c PK sampling.	
 • Plasma concentrations of OG-6219 and FOR-1011 at scheduled assessments using sparse PK sampling during the treatment period. • C_{max}, T_{max}, and AUC_{tau} for both OG-6219 and FOR-1011 on C and C for the population with intensive PK sampling
CCI	

CCI

Note: Refer below and to [Figure 1](#)

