5. To evaluate the change in the PGI-S Score at different time points	
 
Change in PGI-S Score from C to Phone Contact CCI
 

6. To evaluate the change in the PGI-C Score in different time points	
 
Percentage of participants with any improvement on the PGI-C at TRC1, TRC2, and TRC3
 

7. To evaluate the change in the EHP-30 domains (CCI ) from BC to TRC3	
 
Change from BC to TRC3 in the EHP-30 Domain Scores
 

Secondary Safety Endpoints	
8. To assess the incidence of clinically significant b changes from V1 to C in bone biomarkers: 	
 
Mean change from V1 to C in bone biomarker levels
 

9. To assess the incidence of any clinically significant b changes in laboratory parameters from V1 to CC 	
 
Proportion of participants with clinical parameters of significance from V1 to CCI
 

10. To assess vaginal bleeding pattern over the 3 menstrual cycles (TRC1, TRC2, and TRC3) as captured in the eDiary	
 
Mean change from BC to TRC1, TRC2, TRC3 in the number of days on period and number of days with irregular vaginal bleeding/spotting
 

11. To assess any potential change in the ECG parameters at CCI	
 
ECG parameter changes at CCI
 

Secondary PD / PK Endpoints	
12. To assess the change from CCI in serum hormone c concentrations	
 
Mean change from CCI in serum hormone levels
 

13. To assess any difference in serum hormone c concentrations at C between active treatment versus placebo	
 
Serum hormone levels at V5 comparing Group A (CCI BID), B (CCI BID), C (CCI BID) with Group D (Placebo)
 

Version Date: 09JUN2025

- Treatment Cycle 1 is the period between the first day of menses associated with treatment start (C) to the day prior to the first day of next menses, regardless of number of days.
- Treatment Cycle 2 is the period between the first day of second menses after end of BC to the day prior to first day of next menses, regardless of number of days.
- Treatment Cycle 3 or EOT is the period between the first day of third menses after end of BC to either end CCI on study treatment, whichever occurs first.

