## 8.7.6. Other Safety Assessments

### 8.7.6.1. VAGINAL BLEEDING PATTERN

Participants records the presence of bleeding or spotting CCI in the eDiary. The CCI questions to assess bleeding pattern in the eDiary are “1a: During the past 24 hours, did you have any vaginal bleeding or spotting? If the response is “Yes”, then the next question is, “1b: During the past 24 hours, have you been on your period?”.

The following endpoints will be calculated:

- Mean change from BC to TRC1, TRC2, TRC3 in the number of days on period
- Mean change from BC to TRC1, TRC2, TRC3 in the number of days with irregular vaginal bleeding/spotting (i.e. days when question 1a was answered yes and question 1b was answered no)

The definition of cycles for the above endpoints will be different from the definition used for efficacy endpoints. For the vaginal bleeding endpoints, cycles will be defined based on start of menses dates only as below:

- Screening cycle (SC) – starts at the start of menses associated with CCI and ends the day before the start of menses associated with CCI
- Baseline cycle (BC) – starts at the start of menses associated with CCI and ends at the day before the start of menses associated with CCI
- Treatment cycle 1 (TRC1) – starts at start of menses associated with visit 4 and ends the day before the start of menses associated with phone contact C (PC1).
- Treatment cycle 2 (TRC2) – starts at the start of menses associated with phone contact C and ends the day before the start of menses associated with CCI
- Treatment cycle 3 (TRC3) – starts at the start of menses associated with CCI and ends the day before the start of menses associated with CCI
- Safety follow-up cycle (SFC) – starts at the start of menses associated with CCI and ends the day before the start of menses associated with CCI

The following summaries will be provided for vaginal bleeding pattern:

- Observed values and change from BC in the number of days on period by treatment cycle

and by treatment group

- Observed values and change from BC in the number of days with irregular vaginal bleeding/spotting by treatment cycle and by treatment group

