#### 8.7.6.2. ENDOMETRIAL ASSESSMENT: TISSUE COLLECTION AND ULTRASOUND

A Transvaginal Ultrasound or Transabdominal (Pelvic) Ultrasound (TVUS) will be performed at CCI/Screening and CCI / End of TRC3 to assess endometrial thickness and if there is a clinically significant changes in endometrial thickness and histology. Endometrial biopsies are optional for all participants except in the case of abnormal vaginal bleeding (at discretion of the Investigator).

- The following variables will be assessed.
  - Endometrial thickness (mm)
  - Proportion of participants with clinically significant changes from CCI
    - i) In endometrial thickness as assessed by transvaginal ultrasound and
    - ii) Histological findings as assessed by optional endometriosis biopsy (using an endometrial suction curette Pipelle®)

The endometrial thickness will be summarized by treatment group and visit using descriptive statistics of observed data and change from baseline values. Similar analysis for the primary efficacy variable described in Section 8.3.7 using ANCOVA will be performed for the change from baseline to CCI/EOT in endometrial thickness.

The number and percentage of participants with clinically significant changes in endometrial thickness and histology from CCI will be summarized.

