## 10. CHANGES TO PROTOCOL-PLANNED ANALYSES

There were no changes to the analyses planned in the study protocol.

The study protocol did not include a description of the estimand. This has now been included in the SAP.

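### Protocol 9.4.3 points the vaginal bleeding endpoint (secondary safety endpoint 10) to a longitudinal or ANCOVA model, but SAP 8.7.6.1 pre-specifies descriptive summaries only, with no baseline-adjusted dose-minus-placebo difference or interval

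*Protocol*

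**What the plan says.** Protocol 9.4.3 sets the method for secondary endpoints by type of measurement: "Secondary endpoints assessing change in continuous endpoints over time (either measurements within the cycle or at an individual visit) will use longitudinal models" of the kind used for the primary endpoint, and/or ANCOVA. Protocol 9.4.1 says what such models deliver: "All statistical models will evaluate pairwise treatment comparisons between Placebo and a single OG-6219 dose arm". Protocol 9.4.2 gives the output of the longitudinal model: "Estimated treatment differences (each active treatment group versus Placebo) with corresponding 95% CI and 2-sided p-values will also be provided".

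Endpoint 10 sits in the secondary safety block of Protocol Table 1: "Mean change from BC to TRC1, TRC2, TRC3 in the percentage of days with vaginal bleeding". SAP Table 1 restates it as two day counts: "Mean change from BC to TRC1, TRC2, TRC3 in the number of days on period and number of days with irregular vaginal bleeding/spotting".

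For the analysis, SAP 8.7.6.1 lists "Observed values and change from BC in the number of days on period by treatment cycle" and by treatment group, with a matching line for irregular bleeding or spotting. SAP 8.1.1 fixes the content of such a summary as n, mean, SD, median, minimum and maximum, for observed values and for change. The next subsection, 8.7.6.2, says of endometrial thickness: "Similar analysis for the primary efficacy variable described in Section 8.3.7 using ANCOVA will be performed". SAP Section 10 states: "There were no changes to the analyses planned in the study protocol".

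**The concern.** Endpoint 10 is labelled secondary, is a continuous quantity measured per cycle, and is a change from BC at three successive cycles. Protocol 9.4.3 describes that kind of endpoint and gives it a model. The SAP gives it none and does not record the difference.

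The development case for OG-6219 is that it acts locally and leaves the hypothalamic-pituitary-gonadal axis alone (Protocol 2.2 and 4.2). A bleeding comparison with placebo is one of the natural places to look for a departure from that. Under the SAP the report would show four columns of summaries per cycle. It would contain no planned estimate of how far each dose differs from placebo, no planned statement of uncertainty and no adjustment for BC differences between arms. The women contributing would also change from TRC1 to TRC3 as participants stop. SAP Section 2 requires analyses not described in the SAP to be identified as post hoc or unplanned, so a contrast added later would lose its pre-specified status.

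**Working it through.** **1. Does endpoint 10 fall under Protocol 9.4.3?**

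| Feature named in Protocol 9.4.3 | Endpoint 10 |
|---|---|
| Secondary endpoint | Yes, in the secondary safety block |
| Continuous | Yes, as a percentage of days or as day counts |
| Change over time | Yes, BC to TRC1, TRC2 and TRC3 |
| Measured within the cycle | Yes |

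The section heading is not limited to efficacy. Its closing sentence, on definitions for the incidence of clinically significant values, relates to safety endpoints 8 and 9, so the section has safety endpoints in view.

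**2. Is bleeding modelled anywhere else in the SAP?** No. Section 8.4.3 covers pain scores, rescue medication, PGI-S, PGI-C and EHP-30. Section 8.5.3 covers the exploratory efficacy endpoints. The plots of differences from placebo with 95% CIs in 8.1.1 are for the main efficacy analyses.

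**3. The plan's own figure.** No precision is stated for bleeding, so the only figure to reproduce is the power for the primary endpoint in SAP 4.3: 95 per arm, 10% dropout, difference 1, SD 2.2, two-sided alpha 0.05.

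- Evaluable per arm: 95 × 0.9 = 85.5.
- Power = Φ(1 / (2.2 × √(2/85.5)) − 1.96) = Φ(2.97 − 1.96) = 84.4%, or 84.0% with the noncentral t. The stated 84% reproduces.

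This confirms 85.5 per arm as a working number. It has no other bearing on the point.

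**4. Precision for a bleeding contrast.** The documents give no SD or correlation for bleeding days. Both are assumptions here: SD 2.0 days, equal at BC and in the treatment cycle, and BC-to-cycle correlation r of 0.3, 0.5 or 0.7.

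- Common factor: 1.96 × √(2/85.5) = 0.300.
- Unadjusted (difference in raw change): half-width = 0.300 × SD × √(2(1 − r)).
- Baseline-adjusted: half-width = 0.300 × SD × √(1 − r²).
- Variance ratio, adjusted to unadjusted: (1 − r²) / (2(1 − r)) = (1 + r)/2.

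| r | Unadjusted (days) | Adjusted (days) | Variance reduction |
|---|---|---|---|
| 0.3 | 0.71 | 0.57 | 35% |
| 0.5 | 0.60 | 0.52 | 25% |
| 0.7 | 0.46 | 0.43 | 15% |

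Across SD 1.5 to 2.5 days and the same r, the adjusted half-width runs from 0.32 to 0.71 days.

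**5. Number of contrasts added.** 3 doses × 3 cycles × 2 measures = 18.

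**The case against.** A reader might infer a plain breach of the protocol. The documents do not go that far. The synopsis carries the same sentence under its efficacy heading and follows it with a separate primary safety analysis made up of summaries. In Table 1, the line announcing comparison of Groups A, B and C with Group D heads the secondary efficacy block and not the secondary safety block. Protocol 9.1 allows descriptive summaries where appropriate. One subsection of Protocol 9.4.7 is blacked out, and nothing can be inferred from it. These points make the efficacy-only reading arguable. They do not settle it, because the body text of 9.4.3 assigns the method by endpoint type and the sponsor itself models outside efficacy: ANCOVA for the hormones (SAP 8.6.3) and for endometrial thickness (SAP 8.7.6.2).

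A reader might also infer that bleeding was singled out. It was not. Laboratory values, ECG and bone biomarkers are also summarised descriptively, and endometrial thickness is not among the visible secondary safety endpoints 8 to 11. The comparison with 8.7.6.2 shows that a model is feasible in a safety section, not that sibling endpoints are treated unequally.

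Nor is it right that the planned tables cannot show whether a difference is compatible with no effect. The n, mean and SD of change allow an unadjusted difference and interval by hand. What is missing is a planned, baseline-adjusted one.

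Finally, Protocol 2.3.3 says cycle length is monitored through the self-reported bleeding pattern. Days on period and irregular-bleeding days do not measure cycle length, so a model for them would not answer that question.

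**Conclusion.** The point stands as a mismatch between the body of the protocol and the SAP on one secondary safety endpoint. On the more natural reading of Protocol 9.4.3, endpoint 10 should have a model-based comparison with placebo. The SAP omits it without saying so.

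The effect is limited. At r = 0.5 and SD 2 days, adjustment narrows the half-width by 0.08 days (0.60 to 0.52). The larger gain is that an estimate with its uncertainty is fixed in advance. All half-widths rest on the assumed SD and correlation, on the primary endpoint's 10% dropout carrying over, and on roughly normal errors. The last may fail for irregular-bleeding days, which may be mostly zero. A flat claim that the trial can resolve half a bleeding day is therefore not supported. The mismatch itself depends on none of these assumptions, nor on whether bleeding is expressed as a percentage of days or as day counts.

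**What to change.** In SAP 8.7.6.1, keep the descriptive tables and add, in the SAF, a baseline-adjusted model for each bleeding measure. Either use the MMRM of 8.3.5 (BC value, treatment, cycle, treatment-by-cycle) or fit ANCOVA by cycle; Protocol 9.4.3 permits both. The MMRM has the advantage of using all cycles as participants stop. Report each dose-minus-placebo difference with a nominal 95% CI at TRC1, TRC2 and TRC3. For irregular bleeding or spotting days, name a fallback in advance: a robust or bootstrap interval, or a count model, if the Gaussian model fits poorly.

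State that the 18 contrasts are unadjusted for multiplicity and are to be read as estimation, not testing. That added volume is the main downside.

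The cost is one SAP paragraph and reuse of planned code, with no new data. If the sponsor prefers to stay descriptive, SAP Section 10 should say so and give the reason. That would cure the mismatch but not supply the comparison.
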